1.0 Objectives

Primary Objective:

To compare the progression-free survival of adding Pacritinib prior to standard of care allogeneic stem cell transplantation (SOC Allo TP) conditioning with Fludarabine and Busulfan AUC of 4000 microMol-min per day to historical controls in patients with myelofibrosis.

Secondary Objectives:

To evaluate safety and efficacy of this therapy as determined by:

- 1.1 Neutrophil and platelet engraftment.
- 1.2 Non-relapse mortality at one year post transplant.
- 1.3 Overall survival at one year post transplant.
- 1.4 Liver and spleen response to Pacritinib.
- 1.5 Immune recovery.
- 1.6 Quality of life and symptom score.
- 1.7 Primary and secondary graft failure.
- 1.8 Complete remission.
- 1.9 Relapse.

To evaluate the use of marrow specific quantitative MRI (qMRI) sequences in assessment of disease burden, including:

- 1.10 Diffusion-weighted imaging (DWI) with apparent diffusion coefficient (ADP) maps
- 1.11 Marrow fat quantification sequences

2.0 Background

2.1. Overview of the myeloproliferative disorders:

The myeloproliferative disorders (MPD) are chronic hematological malignancies originating at the level of pluripotent hematopoietic stem cells. ^{1,2} The discovery that JAK2 mutations are found in virtually all patients with PV and approximately 50 percent of those with either ET or PMF, has refined current diagnostic criteria in classic MPN

- Polycythemia vera (PV) is considered to be present when an otherwise unexplained increased hematocrit/red blood cell mass is accompanied by the presence of a JAK2 mutation along with a decreased erythropoietin level
- Primary myelofibrosis (agnogenic myeloid metaplasia, chronic idiopathic myelofibrosis) is characterized by the presence of bone marrow fibrosis that cannot be attributed to another myeloid disorder such as CML, PV, ET, or MDS.
- Essential thrombocythemia (ET) is a diagnosis of exclusion, representing clonal or autonomous thrombocytosis not classifiable as PV, PMF, CML, or MDS.

The concepts common to these disorders are:

- 1) Clonal hematopoiesis
- 2) Transformation to acute leukemia (AL): Up to 10% of PV & ET patients develop AL.

3) Progression to myelofibrosis: Up to 10% of patients with ET and PV progress to myelofibrosis with development of massive hepatosplenomegaly, cytopenias and transfusion dependency. Patients who have progressed to myelofibrosis and/or to acute leukemia have a poor prognosis.

2.2. Idiopathic Myelofibrosis:

Idiopathic myelofibrosis (IM) (agnogenic myeloid metaplasia, myelofibrosis with myeloid metaplasia) is a clonal myeloproliferative disorder due to an acquired somatic mutation of a hematopoietic progenitor cell, resulting in clonal erythrocytes, platelets, granulocytes, monocytes and their precursors. These malignant megakaryocytes and monocytes secrete fibrogenic cytokines – TGF, PDGF, FGF, which cause polyclonal fibroblast proliferation, collagen and reticulin deposition, and eventual bone marrow fibrosis, the hallmark of the disease. This process progresses to bone marrow failure and extramedullary hematopoiesis. 1,3,4

The annual incidence of IM ranges from 0.5 –1.5 per 100,000, while the median age at diagnosis is 55-65 years. Most patients with IF present with anemia, marked splenomegaly, early satiety and constitutional symptoms. During the clinical course, most experience progressive anemia requiring frequent blood transfusions, and death occurs eventually due to bone marrow failure or leukemic transformation. Current treatment of IM is palliative, consisting of supportive care with blood transfusions, splenectomy 5, splenic radiation, hydroxyurea, and more recently thalidomide. None of these therapies alters the natural history of this disease.

The median survival is 6.5 years from diagnosis ¹⁰, but varies from 2 years to greater than 10 years depending on presence or absence of well-defined prognostic indicators. A simple but widely accepted scoring system using two of these factors, namely Hb <10 gm/dl and WBC >30,000/l or <4,000/l separates patients into three groups with low (0 factor), intermediate (1 factor), and high (2 factors) risks, associated with a median survival of 93, 26, and 13 months. A more recent study that included anemia (Hb < 10 gm/dl), advanced age (> 64), constitutional symptoms (fever, night sweats, weight loss), leukocytosis (>25,000/l), circulating blasts (≥ 1%), thrombocytopenia, need for blood transfusion and high-risk cytogenetic abnormalities outlines 4 prognostic group with a median survival of 185, 78, 35, and 16 months respectively. Stem cell transplantation is an appropriate option for later two groups. Molecular studies have shown that mutations are present in 31 - 44% patients with myelofibrosis in *ASXL1*, *EZH2*, *SRSF2*, *IDH 1 and 2*, genes. These also have prognostic value independent of International prognostic scoring system with a median survival of 2.6, 7.0, and 12.3 years of 2 or more mutations, 1 mutation, and no mutation in these 5 genes again identifying a poor prognostic subgroup suitable for stem cell transplantation. ^{14,16}

2.3. Allogeneic stem cell transplantation:

Allogeneic hematopoietic cell transplantation by eradicating the malignant clone and restoring normal hematopoiesis is expected to alter the natural history of IM.

Table 1: Allogeneic Transplantation for Myelofibrosis.

Study	N	Median Age	NRM	Median Follow up	os
Guardiola et al ¹⁶	55	42	27%	36 months	47%
Bacigalupo et al ¹⁷	46	51	24%	44 months	45%
Robin et al ¹⁸	147	53	39%	35 months	39%
Patriarca et al ¹⁹	100	49	43%	34 months	42%

Balen et al ²⁰	289	47	35%/50%	41/46 months	37%/30%
Lussana et al ²¹	250	56	28%	13 months	55%*
Kroger et al ²²	103	55	16%	33 months	67%
Ditschkowsk 23	76	45	36%	55 months	53%
Scott ²⁴	170	51	34%	5.9 years	57%
Gupta ²⁵	233	55	24%	50 months	47%
Rondelli et al ²⁶	66	54	22%/59%	24/12 months	75%/32%
Popat et al ²⁷	46	59	13%	25 months	69%

^{*}outcomes for related and unrelated donors respectively, NRM non-relapse mortality, OS overall survival

Due to the uncommon occurrence of this disease and older age at disease onset, majority of studies are small and those that included more than 40 patients are summarized in Table 1. 16,28-31

Transplantation in patients with myelofibrosis is a challenging task. Extramedullary hematopoiesis results in massive hepatosplenomegaly and impaired organ function, making these patients particularly at high risk of graft rejection and treatment related mortality. A special problem area is the treatment of older or debilitated patients. Guardiola published a series of 55 patients demonstrating inferior results for older patients: Five year survival of 14% in patients older than 45 years compared to the 5 year survival of 62% in younger patients. These inferior results in older patients and patients with comorbidity who comprise majority of patients with this disease make myeloablative transplantation a promising but not suitable therapy for most patients with myelofibrosis. Best results of myeloablative transplant using mainly Busulfan and cyclophosphamide regimen in patients with median age of 51 show NRM of 38% and OS of 57%.

Another approach would be to use a reduced intensity or a nonmyeloablative conditioning regimen, which have been reported to extend allogeneic transplant to older patients and patients with other co-morbid medical conditions. We, and others, have shown that reduced intensity stem cell transplantation can be safely utilized in older patients and those with comorbidities in other hematological malignancies. 32-37 Rondelli et al and Kroger et al have reported encouraging data in multi-institutional small studies of reduced intensity transplantation in older patients with myelofibrosis. 30,31 In these retrospective studies with a median age of 54 years, a non-relapse mortality of 10% - 16% and 3 year overall survival of 84% - 85% was reported. Based on these data multiple centers studied reduced intensity allogeneic transplantation in myelofibrosis. Recent analysis of worldwide experience reported to CIBMTR registry showed NRM of 24% and OS of 47% ²⁵. Outcome was significantly inferior with unrelated donor. Similarly high NRM of 53% was reported with unrelated donors in a prospective study done by MPD research consortium. Best results to date with reduced intensity regimen were reported by Kroger et al. NRM was 16% and OS 67% with Busulfan and Fludarabine regimen: however 17% of patients had low risk disease and hence expected to have better outcome. Moreover, 13% of patients needed stem cell boost for graft failure or weak graft or declining chimerism. 31

2.4 Allogeneic transplantation for Myelofibrosis: M D Anderson data:

At MDACC based on encouraging early data, 30,31 we did a prospective study to evaluate the role of allogeneic stem cell transplantation using reduced intensity conditioning regimen of

[figure not shown]

Myelofibrosis results in extramedullary hematopoiesis, massive hepatosplenomegaly and fibrosis in the marrow and there are several major issues unique to it from transplant perspective. These include high incidence of graft failure and weak graft after transplant necessitating use of stem cell boost²² and organ dysfunction - particularly involving liver - leading to a high incidence of veno-occlusive disease and non-relapse mortality.⁴⁰ A safe agent that can reduce organomegaly and disease burden pretransplant may improve transplant outcome by improving engraftment, reducing organ toxicity and lowering relapse risk. Furthermore, it may allow more patients to become eligible for transplant by improving their performance status. A Jak 2 inhibitor might be the answer.

Jak 2 inhibitors and stem cell transplantation:

Discovery of Jak2 V617F mutation, which makes kinase constitutionally active in patients with myeloproliferative disorders led to development several targeted agents including Pacritinib to inhibit this pathway. Jak 2 is mutated in up 60% of patients with ET and MF and 98% of patients with PV. Even in patients without this mutation, this pathway is overactive. Ruxolitinib, a Jak2 inhibitor, is licensed by FDA for MF reduces splenomegaly, improves constitutional symptoms, and improves survival both in patients with and without Jak 2 V617F. Early data on its usage pre-transplant are conflicting with excellent outcome reported in some studies, but a possible higher complication rate reported in other study. This later study presented as an abstract is difficult to interpret, because complications reported are hard to differentiate from usual complications seen post-transplant. Pacritinib causes less myelosuppression than Ruxolitinib and may be superior to ruxolitinib as a pre-transplant agent to reduce organomegaly and to reduce the disease burden.

Pacritinib:

Pacritinib, a Jak2/Flt 3 inhibitor, has activity in myeloid and lymphoid malignancies. Currently it is in Phase 3 studies in patients with myelofibrosis. Details of this molecule are in the attached investigator brochure and a brief summary follows. It is a potent selective inhibitor of mutant as well as normal Jak2 kinase. Preclinical studies showed its activity in suppressing Jak 2 mediated tumors. PK studies in clinical trials showed slow absorption (Tmax 4-6 hours) and dose related increase in systemic exposure up to 400 mg per day. Terminal elimination half-life was 47 hours. Food did not impair absorption. At 100 mg/day dose steady state levels exceeded IC50 values for inhibition of Jak2/Flt3 kinase. Phase I studies identified 400 mg daily as dose for further studies. Dose limiting toxicity included grade 3 QTc prolongation, grade 3 diarrhea and grade 2 dizziness and blurred vision. Most common adverse events occurring in more than 20% were diarrhea, nausea, vomiting, constipation, dyspnea, fatigue and edema. Most events were mild to moderate severity. Only grade 3 or higher adverse event occurring in more than 10% of patients were anemia or thrombocytopenia (16%). MRI showed ≥ 25% spleen volume reduction in 55% of patients. An improvement in all symptoms relevant to myelofibrosis was seen. Thus, Pacritinib is very safe and highly effective therapy for patients with myelofibrosis and we would like study its role pre-transplant to improve transplant outcomes.

Correlative Research Studies (optional):

To evaluate the effect of the JAK2 inhibitor Pacritinib on immune recovery and graft-versus-host disease post-transplant

Janus kinase-2 (JAK2) conveys receptor-binding signals by several inflammatory cytokines, via phosphorylation of STAT3. Selective inhibition of JAK2 was shown to induce tolerance to allo-antigens, while preserving de novo responses to pathogens 48. Selective JAK2 inhibition was also shown to preserve Treg numbers through preservation of the IL-15/JAK3/pSTAT5 pathway.

Signaling through IFN γ -receptor, mediated by JAK1/JAK2 and STAT1, has been shown to result in increased surface expression of CXCR3, a key chemokine receptor involved in T-cell trafficking to sites of inflammation. A recent study in a murine model of GVHD, showed that pharmacologic inhibition of IFN γ R signaling with inhibitors of JAK1/JAK2 resulted in decreased expression of CXCR3 associated with reduced GVHD, mediated by altered trafficking of effector T cells to GVHD target organs, ⁴⁹ providing another mechanism through which selective JAK2 inhibition could influence GVHD.

We *hypothesize* that the Jak 2 inhibitor, Pacritinib will reduce the risk of GVHD in patients with myelofibrosis undergoing allogeneic stem cell transplantation, resulting in improved survival.

To test this hypothesis we propose the following aims:

Aim 1: To determine how Pacritinib affects the balance of Treg/Th1/Th2/Th17 cells. T cells collected at multiple time points before and during therapy (as outlined below) will be activated via CD3/TCR and CD28 ligation and differentiated according to their cytokine profile into Th1 (CD4+IFN- γ +), Th2 (CD4+IL-4+), Th17 (CD4+IL-17+) and Tr1 (CD4+IL-10+). Naturally occurring Tregs will be defined as CD4+CD25hiFoxp3+CD127lo.

Aim 2: To determine how Pacritinib influences the expression of chemokine receptors on the surface of T cells, including CXCR2, CXCR3, CXCR4, CXCR5, CCR3, CCR4, CCR5, CCR6,

CCR7, and CCR9

Aim 3: To determine how Pacritinib influences the pathogen-specific immune responses.

We will conduct analyses of T cell phenotype, estimate antigen-specific T cell precursor frequencies (by intracellular cytokine flow cytometry and peptide/dextramer staining) and determine antigen-specific cytokine production capacity (cytokine bead array assay). We will perform:

- Immunophenotypic recovery of naive, stem-like memory, central and effector memory CD4+ and CD8+ T cells, using a 10 color flow cytometry panel (CD3, CD4, CD8, CD45RA, CD45RO, CCR7, CD62L, CD95, IL-7Rα, IL-2Rα);
- 2) The number and function of recovering CMV, T cells capable of responding functionally to in vitro stimulation with overlapping pools of peptide by intracellular cytokine detection. ^{3,5,6}

Aim 4: To determine how Pacritinib influences the phenotype and function of dendritic cells (DCs).

We will characterize DC subsets in PB collected at multiple time points before and during therapy (as outlined below) by:

- 1) Analysis of DC subsets, myeloid/plasmacytoid and immature/mature, based on expression of CD3, CD4, CD14, CD123, CD11c, CD1a, CD1c and CD141;
- 2) Determining the expression of DC co-stimulatory molecules involved in APC function (HLA-DR, CD80, CD83, and CD86) and chemokine receptors involved in DC homing (CCR4, CCR5, CXCR3, CCR10).

Serum samples collected from patients will be assayed for cytokine levels using the BD Cytometric Bead Array for Th1/Th2 cytokines (IL-2, IL-4, IL-5, IL-6, IL-10, TNF, IFN- γ) and for inflammation (IL-8, IL-1 β , IL-6, IL-10, TNF, IL-12 ρ 70).

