6.0 Statistical Considerations

General

This will be a single-arm, Phase II study of pacritinib, fludarabine, and busulfan as a preparative

regimen in allogeneic stem cell transplantation in patients with myelofibrosis. The primary endpoint is progression-free survival (PFS) in patients undergoing matched related or at least 7/8 matched unrelated donor transplant. We will enroll at least 21 evaluable patients, defined as patients who undergo transplant with a matched related or at least 7/8 matched unrelated donor. Patients who do not have a suitable related or unrelated donor will come off study and may receive a transplant from a haploidentical donor. For this reason and because some patients may decide not to undergo transplant after starting the drug, we may need to enroll up to 40 patients to ensure that 21 are evaluable for our primary endpoint.

Endpoints

6.1 Primary End Point (Progression-Free Survival):

Progression-free survival is defined as the time of stem-cell transplant to the time of death or disease progression.

6.2 Secondary End Points:

Neutrophil Engraftment is defined as a sustained ANC \geq 0.5 x 10 $^{\circ}$ /L for 3 consecutive days and evidence of donor chimerism by D+28 (the first chimerism study will be done 3-4 weeks post-transplant).

Platelet Engraftment is defined as a sustained first of three consecutive laboratory values of platelet $\geq 20x109/L$ with no platelet transfusions administered for 7 consecutive days.

Non-relapse mortality is defined as death without disease progression.

Liver response will be defined by the change in the size of the liver measured below the coastal margin in the mid-clavicular line by palpitation.

Spleen response will be defined by the change in the size of the spleen measured below the coastal margin in the mid-clavicular line by palpitation.

Quality of life will be measured by the QOL FACT BMT.

Symptom score will be measured by the MPD symptom score.

Immune recovery will be measured by various cell subsets and cytokine levels.

Primary Graft Failure is defined as failure to achieve an ANC \geq 0.5 x 10 $^{\circ}$ /L for 3 consecutive days by day 28, with <10% cellularity on bone marrow biopsy and no evidence of donor chimerism.

Secondary graft failure is defined as a sustained declined of ANC <0.5 x 10°/L for 3 consecutive days after initial documented engraftment with no evidence of disease progression.

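### The engraftment and graft failure endpoints do not say how a stem cell boost is handled, so a patient boosted before meeting a failure definition is scored as engrafted and free of graft failure

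*Combined protocol and SAP*

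**What the plan says.** Section 2.4, under the major impediments to transplant, says of the issues particular to this disease: "These include high incidence of graft failure and weak graft after transplant necessitating use of stem cell boost". It then argues that a safe agent given before transplant "may improve transplant outcome by improving engraftment, reducing organ toxicity and lowering relapse risk". Section 2.3 gives one figure for boost use, from the series it regards as the best reduced-intensity result so far: "13% of patients needed stem cell boost for graft failure or weak graft or declining chimerism".

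Section 1.0 makes neutrophil and platelet engraftment (1.1) and primary and secondary graft failure (1.7) secondary objectives. Section 6.2 defines them as follows.

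- **Neutrophil engraftment:** ANC of at least 0.5 "for 3 consecutive days and evidence of donor chimerism by D+28".
- **Platelet engraftment:** the first of three consecutive values at or above 20, "with no platelet transfusions administered for 7 consecutive days". There is no day limit.
- **Primary graft failure:** no ANC recovery by day 28, together "with <10% cellularity on bone marrow biopsy and no evidence of donor chimerism".
- **Secondary graft failure:** ANC below 0.5 for 3 consecutive days "after initial documented engraftment with no evidence of disease progression".

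None of the four refers to a boost or second infusion. Under Secondary Analyses, times to neutrophil and platelet engraftment are estimated by Kaplan-Meier. Boosts do not appear among the objectives, the evaluations in Section 5, the endpoints and analyses in Section 6, or the adverse event rules in Section 8.

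**The concern.** A boost is a rescue for a graft that is not performing. If the endpoint rules ignore it, recovery obtained with the rescue is credited to the original graft, and a patient rescued early enough never reaches a failure criterion. Of the three reasons for boosting that Section 2.3 lists, weak graft and declining chimerism have no endpoint of their own in Section 6.2.

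The effect is in the flattering direction, on the outcomes through which the rationale expects benefit. A trial in which a few patients needed a boost could report complete engraftment and no graft failure without breaking any of its own rules. If no rule is fixed in advance, the handling of these patients would be settled after the results are known.

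**Working it through.** **1. Apply Section 6.2 literally to each type of boosted patient.**

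| Patient | Scored under Section 6.2 |
|---|---|
| Meets all three primary failure criteria at day 28, then boosted | Primary graft failure; a later rescue does not cancel it |
| Engrafts, ANC then below 0.5 for 3 days without progression, then boosted | Secondary graft failure; a later rescue does not cancel it |
| Engrafts, later boosted for weak graft or declining chimerism with ANC staying at or above 0.5 | Engrafted, no graft failure; boost invisible |
| Neutrophils engrafted, boosted before platelet recovery, platelets then recover | Platelet engraftment, no graft failure |
| Boosted before day 28, ANC and donor chimerism then present by day 28 | Neutrophil engraftment, no primary failure |

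The first two rows are counted properly as failures. The last three are the gap. In the third row the engraftment already documented is genuine, and what is lost is the boost. In the last two rows the engraftment itself depends on the boost.

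**2. What is required to be captured.** Section 8.1 limits entry in PDMS/CORe to pacritinib-related adverse events and data specific to the protocol. Section 8 also keeps adverse events known to be related to the standard transplant out of PDMS, and the list that follows includes graft failure. Graft failure can still enter as an endpoint. Boosts belong to no endpoint, so nothing in the text makes them protocol-specific data.

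**3. The plan's own figure.** Section 6 gives 21 evaluable patients for 1-year PFS of 61% versus 80%, one-sided 5%, 80% power, 3 years of accrual and 1 further year of follow-up. With hazards l0 = -ln 0.61 = 0.494 and l1 = -ln 0.80 = 0.223, and event probabilities P0 = 0.682 and P1 = 0.417 under uniform accrual:

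N = [(1.645 × l0/√P0 + 0.842 × l1/√P1) / (l0 - l1)]² = 22.1.

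The cube-root scale gives 18.3. The stated 21 lies within the range of standard variants. It serves here only as the denominator, and nothing below depends on how it was derived.

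**4. Expected number of boosts.** Assume each of n = 21 patients has probability p of a boost. The documents give no boost rate for this trial or for the institution's own historical cohort, so p = 0.13 is borrowed from the series in Section 2.3, with 0.05 to 0.20 as an assumed range.

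- Expected number = 21p
- P(at least one) = 1 - (1 - p)^21
- P(at least two) = 1 - (1 - p)^21 - 21p(1 - p)^20

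| p | Expected | P(≥1) | P(≥2) |
|---|---|---|---|
| 0.05 | 1.1 | 66% | 28% |
| 0.13 | 2.7 | 95% | 78% |
| 0.20 | 4.2 | 99% | 94% |

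**5. Effect on a reported rate.** One patient is 1/21 = 4.8 percentage points. If every boost hid a failure, the graft failure rate would be understated by 2.73/21 = 13 points. That is a ceiling, because boosts given after a failure definition is met (rows 1 and 2 of the first table) hide nothing.

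**6. Precision.** An observed 3/21 (14.3%) has an exact 95% CI of 3.0% to 36.3%, so the boost proportion can only be descriptive.

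**The case against.** A reader might infer that every rescued patient is scored as a success. The definitions do not support that: nothing in Section 6.2 removes graft failure status once a criterion has been met.

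A reader might also infer that boosts will go unrecorded. That is partly an inference from silence. Section 5.4.1 leaves post-transplant evaluation to standard practice, Section 4.8 describes a departmental database that may well hold boost data, the exclusion in Section 5.2 concerns medications, and the case report form and appendices are not part of the text reviewed. What stands is narrower: no provision requires boosts to be extracted, coded by reason or analysed.

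Nor does the plan promise fewer boosts. Section 2.4 hopes for better engraftment, and the declared comparator is the institution's own cohort, for which no boost rate is given. The 13% comes from a series that Section 2.3 describes as including 17% low-risk patients, whom this trial excludes. It is a planning figure, not a benchmark to be tested against.

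Three technical objections deserve weight.

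- A time-to-event endpoint needs no day limit, and late platelet recovery appears as late recovery on the curve. True, but the recovery is still counted as an event of the original graft.
- No passage describes boosts before day 28, so the last row of the first table is hypothetical. The weak-graft and platelet rows do not depend on it.
- Weak graft with ANC at or above 0.5 is simply not graft failure under the stated definition, and applying a stated definition is not in itself bias. This is accepted, and it is why the strict definitions should stay, with boosts reported beside them.

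Finally, these are secondary endpoints in a single arm with no hypothesis test specified for them. That limits the weight of the point but does not remove it.

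**Conclusion.** The point holds in this form: the plan names weak graft needing a boost as a major problem, then leaves boosts out of both data requirements and endpoint rules, so a patient boosted before meeting a failure definition is scored as engrafted and free of graft failure. Patients who meet a definition first are counted correctly.

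At an assumed 13%, about 2.7 of 21 patients would be boosted and at least one boost is likely (95%); the expected number is 1.1 to 4.2 over 5% to 20%. It would be tempting to say that graft failure is understated by 13 points. The documents do not support that, because Section 2.3 gives no split of its 13% by reason or timing, and the misclassified share cannot be calculated. Thirteen points is only the upper bound at that rate.

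The consequence is confined to objectives 1.1 and 1.7. PFS counts death or progression and does not depend on boosts, so neither the primary test nor N = 21 changes. The matter is worth correcting because the omission favours the treatment rationale and the correction is cheap.

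**What to change.** 1. Record the date and reason of every stem cell boost or second graft infusion, and designate these as protocol-specific data so that they are entered in the trial database.
2. In Section 6.2, state that neutrophil or platelet recovery first reached after a boost or second infusion is not counted as engraftment from the original graft. Engraftment documented before a boost stands.
3. In Secondary Analyses, treat a boost before recovery as a competing event and replace the Kaplan-Meier estimates of time to neutrophil and platelet engraftment with cumulative incidence. The plan already uses a competing-risks framework for non-relapse mortality and relapse.
4. Keep the primary and secondary graft failure definitions unchanged. Beside them, as a supplementary summary, report the proportion boosted by reason with an exact 95% CI.

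The cost is a date and a reason field, a few lines in Section 6.2, and one change of estimator. The downside is that reported engraftment may be slightly lower. The change concerns only what is counted and says nothing about when a boost should be given.
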